**Table 6.3: Dose Reductions for the Up-titration Dose Regimen**

Starting Dose (0)	6.4 mg/kg IV Q3W	4.8 mg/kg Q3W	3.2 mg/kg Q3W
Dose Level (- 1)	4.8 mg/kg IV Q3W	3.2 mg/kg Q3W	Discontinue
Dose Level (- 2)	3.2 mg/kg IV Q3W	Discontinue	Discontinue

IV = intravenous; Q3W = every 3 weeks.

Subjects will be withdrawn from the study treatment if further toxicity meeting the requirement for dose reduction occurs.

### Dose Modification Guidelines

[Table 6.4](#) provides schedule modifications for specific toxicities.

Fatigue/Asthenia/Malaise	Grade 3	
Delay dose until resolved to ≤Grade 1, then:
 
 
• If resolved to ≤Grade 1 or baseline values in ≤14 days, resume patritumab deruxtecan;
 
• If resolved to ≤Grade 1 or baseline values in >14 days, reduce patritumab deruxtecan by 1 dose level and resume.
 

Blood and lymphatic system disorders		
Neutrophil count decreased	Grade 3 (500 to <1000/mm  ; 0.5-1 × 10  /L)	Delay dose until resolved to ≤Grade 2, then resume patritumab deruxtecan.
	Grade 4 (<500/mm  ; <0.5 × 10  /L)	Delay dose until resolved to ≤Grade 2; then reduce patritumab deruxtecan by 1 dose level.

	Worst Toxicity NCI-CTCAE v5.0 Grade (unless otherwise specified)	Schedule Modification for Patritumab Deruxtecan
Febrile neutropenia (ANC <1000/mm^3; <1 × 10^9/L, fever >38.3°C or a sustained temperature of ≥38°C for more than 1 hour)	Grade 3	Delay dose until resolved; then resume patritumab deruxtecan. Consider reducing patritumab deruxtecan by 1 dose level.  Consider administration of G-CSF as prophylaxis for all subsequent cycles and according to local guidelines.
Febrile neutropenia (ANC <1000/mm^3; <1 × 10^9/L, fever >38.3°C or a sustained temperature of ≥38°C for more than 1 hour)	Grade 4	Delay dose until resolved, then reduce patritumab deruxtecan by 1 dose level and resume.  Administer G-CSF as prophylaxis for all subsequent cycles and according to local guidelines.
Lymphocyte count decreaseda	Grade 4 (<0.2 × 10  /L)	Delay dose until resolved to ≤Grade 2, then: 
 
• If resolved in ≤14 days, resume patritumab deruxtecan.
 
• If resolved in >14 days; reduce patritumab deruxtecan by 1 dose level and resume.
 

Anemia	Grade 3 (Hemoglobin <8.0 g/dL)	Delay dose until resolved to ≤Grade 2 or baseline; then resume patritumab deruxtecan.  For recurrent anemia, delay dose until resolved ≤Grade 2 or baseline, then reduce patritumab deruxtecan by 1 dose level and resume.  Consider transfusion per institutional guidelines.
	Grade 4 (Life-threatening consequences; urgent intervention indicated)	Delay dose until resolved to ≤Grade 2 or baseline, then reduce patritumab deruxtecan by 1 dose level and resume.  Consider transfusion per institutional guidelines.
Platelet count decreased	Grade 3 (Platelet <50 – 25 × 10  /L)	Delay dose until resolved to ≤Grade 1, then: 
 
• If resolved in ≤14 days, resume patritumab deruxtecan;
 
• If resolved in >14 days, patritumab deruxtecan may be resumed. Consider reducing patritumab deruxtecan by 1 dose level.
 
 Consider transfusion per institutional guidelines.
	Grade 4 (Platelet <25 × 10  /L)	Delay dose until resolved to ≤Grade 1, then reduce patritumab deruxtecan by 1 dose level and resume.  Consider transfusion per institutional guidelines.

	Worst Toxicity NCI-CTCAE v5.0 Grade (unless otherwise specified)	Schedule Modification for Patritumab Deruxtecan
Cardiac disorders		
Heart failure	Grade $\geq 2$ (Symptoms with moderate activity or exertion)	Cardiologist consultation as necessary. Delay dose until resolved to $\leq$ Grade 1, then reduce patritumab deruxtecan by 1 dose level.
Ejection fraction decreased	Decrease in LVEF 10% to 20% (absolute value), but LVEF $>45\%$	Continue patritumab deruxtecan.
	LVEF 40% to $\leq 45\%$ and decrease is $<10\%$ (absolute value) from baseline	Continue patritumab deruxtecan. Repeat LVEF assessment within 3 weeks.
	LVEF 40% to $\leq 45\%$ and decrease is $\geq 10\%$ to 20% (absolute value) from baseline	Delay patritumab deruxtecan. Repeat LVEF assessment within 3 weeks. If LVEF has not recovered to within 10% (absolute value) from baseline, discontinue subject from study treatment.
	LVEF $<40\%$ or $>20\%$ (absolute value) drop from baseline	Delay patritumab deruxtecan. Repeat LVEF assessment within 3 weeks. If LVEF $<40\%$ or $>20\%$ (absolute value) drop from baseline is confirmed, discontinue patritumab deruxtecan. Cardiologist consultation as necessary.
Electrocardiogram QT corrected interval prolonged	Grade 3 (Average QTcF $\geq 501$ ms; $>60$ ms change from baseline)	Delay patritumab deruxtecan until resolved to $\leq$ Grade 1 (QTcF $\leq 480$ ms). Determine if another medication the subject was taking may be responsible and can be adjusted or if there are any changes in serum electrolytes that can be corrected. If QTcF prolongation is attributed to patritumab deruxtecan, then reduce patritumab deruxtecan by 1 dose level. Cardiologist consultation as necessary.
	Grade 4 (Torsades de pointes; polymorphic ventricular tachycardia; signs/symptoms of serious arrhythmia)	Discontinue subject from patritumab deruxtecan. Cardiologist consult as necessary.

	Worst Toxicity NCI-CTCAE v5.0 Grade (unless otherwise specified)	Schedule Modification for Patritumab Deruxtecan
Respiratory, thoracic and mediastinal disorders		
Pulmonary toxicity	See next column	
If a subject develops radiographic changes potentially consistent with ILD or develops an acute onset of new or worsening pulmonary or other related signs/symptoms such as dyspnea, cough or fever, rule out ILD.
 
If ILD is suspected, delay patritumab deruxtecan dosing pending further evaluation and start corticosteroid treatment promptly unless clinically contraindicated.
 
Evaluations must include CT (preferably high-resolution CT), and pulmonologist consultation (when the Investigator is not a pulmonologist). The following evaluations must also be obtained, as indicated:
 
 
• Infectious disease consultation as clinically indicated
 
• Blood culture and CBC (other blood tests could be considered as needed)
 
• Bronchoscopy and bronchoalveolar lavage if clinically indicated and feasible
 
• Pulmonary function tests
 
• Pulse oximetry (SpO2)
 
• Arterial blood gases, as clinically indicated
 
• Diffusing capacity of the lungs for carbon monoxide (DLCO), as clinically indicated
 
• One blood sample collection for PK analysis as soon as ILD is suspected, if feasible
 
• Other tests, as clinically indicated
 
 
If a non-inflammatory/infectious etiology is confirmed by the Investigator, treat accordingly and resumption of patritumab deruxtecan may occur after discussion between the Investigator and Sponsor.
 
All events of ILD regardless of severity or seriousness will be followed until resolution including after drug discontinuation.

	Worst Toxicity NCI-CTCAE v5.0 Grade (unless otherwise specified)	Schedule Modification for Patritumab Deruxtecan
	Grade 1	
The administration of patritumab deruxtecan must be delayed. Patritumab deruxtecan can be restarted only if the event is fully resolved to Grade 0:
 
 
• If resolved in <math>\leq 28</math> days from day of onset, maintain dose.
 
• If resolved in <math>> 28</math> days from day of onset, reduce dose 1 level.
 
 
Toxicity Management:
 
 
• Monitor and closely follow-up in 2 to 7 days for onset of clinical symptoms and pulse oximetry.
 
• Consider follow-up imaging in 1-2 weeks (or as clinically indicated).
 
• Consider starting systemic steroids (eg, at least 0.5 mg/kg/day prednisone or equivalent) until improvement, followed by gradual taper over at least 4 weeks.
 
• If worsening of diagnostic observations despite initiation of corticosteroids, then follow Grade 2 guidelines (if subject is asymptomatic, then subject must still be considered as Grade 1 even if steroid treatment is given).
 

	Grade 2	
Permanently discontinue subject from study treatment.
 
Toxicity Management:
 
 
• Promptly start systemic steroids (eg, at least 1 mg/kg/day prednisone or equivalent) for a minimum of 14 days or until complete resolution of clinical symptoms and chest CT findings, followed by gradual taper over at least 4 weeks.
 
• Monitor symptoms closely.
 
• Re-image as clinically indicated.
 
• If worsening or no improvement in clinical or diagnostic observations in 5 days, 
 
– Consider increasing dose of steroids (eg, 2 mg/kg/day prednisone or equivalent) and administration may be switched IV (eg, methylprednisolone).
 
– Re-consider additional work-up for alternative etiologies as described above.
 
– Escalate care as clinically indicated.
 
 
 

	Worst Toxicity NCI-CTCAE v5.0 Grade (unless otherwise specified)	Schedule Modification for Patritumab Deruxtecan
	Grade 3 or 4	
Permanently discontinue subject from study treatment.
 
Toxicity Management:
 
 
• Hospitalization required.
 
• Promptly initiate empiric high-dose methylprednisolone IV treatment (eg, 500-1000 mg/day for 3 days), followed by at least 1.0 mg/kg/day of prednisone (or equivalent) for a minimum of 14 days or until complete resolution of clinical symptoms and chest CT findings, followed by gradual taper over at least 4 weeks.
 
• Re-image as clinically indicated.
 
• If still no improvement within 3 to 5 days, 
 
– Re-consider additional work-up for alternative etiologies as described above.
 
 
 
 
Consider other immuno-suppressants and/or treat per local practice.

Eye disorders		
Ocular	Grade 3	
Delay dose until resolved to <math>\leq</math>Grade 2, then:
 
 
• If resolved in <math>\leq</math>7 days, resume patritumab deruxtecan;
 
• If resolved in <math>></math>7 days, then reduce patritumab deruxtecan by 1 dose level.
 
 
Ophthalmologist consultation as necessary.

	Grade 4	
Discontinue subject from patritumab deruxtecan.
 
Ophthalmologist consultation as necessary.

Renal and urinary disorders		
Creatinine increased	Grade 3 ( $>3.0 \times$ baseline; $>3.0 - 6.0 \times$ ULN)	
Delay dose until resolved to <math>\leq</math>Grade 1 or baseline, then reduce patritumab deruxtecan by 1 dose level.

	Grade 4 ( $>6.0 \times$ ULN)	
Discontinue subject from patritumab deruxtecan.

	Worst Toxicity NCI-CTCAE v5.0 Grade (unless otherwise specified)	Schedule Modification for Patritumab Deruxtecan
Hepatobiliary disorders		
AST or ALT increased without total bilirubin (TBL) increased	Grade 2 (>3.0 - 5.0 × ULN if baseline was normal; >3.0 - 5.0 × baseline if baseline was abnormal)	Continue patritumab deruxtecan. In subjects without liver metastasis, monitor AST/ALT 24 to 72 hours later, and continue regular monitoring until resolution.
	Grade 3 (>5.0 – 20.0 × ULN if baseline was normal; >5.0 - 20.0 × baseline if baseline was abnormal) In subjects without liver metastases and subjects with liver metastases and baseline level ≤ 3 x ULN.	Delay patritumab deruxtecan dose until resolved to ≤Grade 1, then: 
 
• If resolved in ≤7 days, resume patritumab deruxtecan;
 
• If resolved in >7 days, then reduce patritumab deruxtecan by 1 dose level.
 

	>8.0 - 20.0 x ULN if baseline was normal; >8.0 - 20.0 x baseline if baseline was abnormal In subjects with liver metastases, if the baseline level was > 3 x ULN.	Delay patritumab deruxtecan dose until resolved to ≤baseline level, then: 
 
• If resolved in ≤7 days, resume patritumab deruxtecan;
 
• If resolved in >7 days, then reduce patritumab deruxtecan by 1 dose level.
 

	Grade 4 (>20.0 × ULN if baseline was normal; >20.0 × baseline if baseline was abnormal)	Discontinue subject from patritumab deruxtecan. Gastroenterologist or hepatologist consultation as necessary.
TBL increased	Grade 2 (>1.5 – 3.0 × ULN if baseline was normal; >1.5 - 3.0 × baseline if baseline was abnormal).	If no documented Gilbert’s syndrome or liver metastases at baseline, delay patritumab deruxtecan until resolved to ≤Grade 1, then: 
 
• If resolved in ≤7 days, resume patritumab deruxtecan;
 
• If resolved in >7 days, reduce patritumab deruxtecan by 1 dose level.
 
 If documented Gilbert’s syndrome or liver metastases at baseline, continue patritumab deruxtecan.

	Worst Toxicity NCI-CTCAE v5.0 Grade (unless otherwise specified)	Schedule Modification for Patritumab Deruxtecan
	Grade 3 (>3.0 – 10.0 × ULN if baseline was normal; >3.0 - 10.0 × baseline if baseline was abnormal)	
If no documented Gilbert’s syndrome or liver metastases at baseline, delay patritumab deruxtecan dose until resolved to ≤Grade 1, then:
 
 
• If resolved in ≤7 days, reduce patritumab deruxtecan by 1 dose level;
 
• If resolved in >7 days, discontinue subject from patritumab deruxtecan.
 
 
If documented Gilbert’s syndrome or liver metastases at baseline, delay patritumab deruxtecan dose until resolved to ≤Grade 2, then:
 
 
• If resolved in ≤7 days, reduce patritumab deruxtecan by 1 dose level;
 
• If resolved in >7 days, discontinue subject from patritumab deruxtecan.
 

	Grade 4 (>10.0 × ULN if baseline was normal; >10.0 × baseline if baseline was abnormal)	Discontinue subject from patritumab deruxtecan.
AST or ALT increased and TBL increased	AST or ALT ≥3 × ULN with simultaneous TBL >2 × ULN	
Delay patritumab deruxtecan until drug-induced liver injury can be ruled out. The Investigator must consult with a gastroenterologist or hepatologist as needed, and the subject must be treated accordingly.
 
Monitor AST/ALT and TBL twice weekly until resolution or return to baseline.
 
It is strongly recommended to perform a full diagnostic workup to exclude alternative causes, such as viral or autoimmune hepatitis, alcoholic liver injury, biliary tract disorders, or hemodynamic abnormalities. Results from diagnostic workup (including, for example: INR, direct bilirubin, serologic tests for hepatitis A, B, and C; alcohol use, ultrasound, MRI, CT scan, concomitant medication use, immunoglobulin levels, ECHO) must be recorded within the eCRF.
 
If drug-induced liver injury is ruled out, the subject must be treated accordingly, and resumption of patritumab deruxtecan may occur after discussion between the Investigator and Sponsor.
 
Patritumab deruxtecan will be permanently discontinued if drug-induced liver injury cannot be ruled out from diagnostic workup.

	Worst Toxicity NCI-CTCAE v5.0 Grade (unless otherwise specified)	Schedule Modification for Patritumab Deruxtecan
AST or ALT > 3.0 x ULN (if liver metastases are present, >5 xULN) with known Hepatitis B and/or Hepatitis C infection at baseline	--	
Delay patritumab deruxtecan until reactivation of Hepatitis B and/or Hepatitis C can be ruled out.
 
Perform HBV DNA and/or HCV RNA to rule out reactivation of Hepatitis B and/or Hepatitis C, respectively.
 
Hepatologist and infectious disease consultations are recommended.
 
If reactivation of Hepatitis B and/or Hepatitis C is confirmed, permanently discontinue patritumab deruxtecan.

Gastrointestinal disorders		
Nausea	Grade 3 (inadequate oral caloric or fluid intake; tube feeding, total parenteral nutrition [TPN], or hospitalization indicated)	
Delay patritumab deruxtecan until resolved to ≤ Grade 1, and consider treatment with anti-emetics and/or corticosteroids as per Investigators judgement and local practice/guidelines, then:
 
 
• If resolved to ≤Grade 1 in ≤14 days, resume patritumab deruxtecan.
 
• If does not resolve to ≤Grade 1 in >14 days, reduce patritumab deruxtecan by 1 dose level.
 

Vomiting	Grade 3 (tube feeding, TPN, or hospitalization indicated)	
Delay patritumab deruxtecan until resolved to ≤Grade 1, and consider treatment with anti-emetics and/or corticosteroids as per Investigators judgement and local practice/guidelines, then:
 
 
• If resolved to ≤Grade 1 in ≤7 days, resume patritumab deruxtecan;
 
• If does not resolve to ≤Grade 1 in >7 days, reduce patritumab deruxtecan by 1 dose level.
 

	Grade ≥4	Discontinue subject from patritumab deruxtecan

Based on currently available clinical safety data for patritumab deruxtecan, it is recommended that subjects receive premedication with antiemetic agents. Suggested agents include a 5-HT3 blocker in combination with another antiemetic or corticosteroid approximately 30 minutes prior to patritumab deruxtecan infusion. Choice of agents is based on Investigator's discretion as per local/institutional guidelines. Investigators must also consider providing subjects with an antiemetic regimen for subsequent use as needed.
		
Diarrhea/Colitis	Grade 3	
Delay patritumab deruxtecan until resolved to ≤Grade 1, and consider treatment per local practice/guidelines, then:
 
 
• If resolved to ≤Grade 1 in ≤7 days, resume patritumab deruxtecan;
 
• If resolved to ≤Grade 1 in >7 days, then reduce patritumab deruxtecan by 1 dose level.
 

	Grade 4 (Life-threatening consequences; urgent intervention indicated)	Discontinue subject from patritumab deruxtecan.

	Worst Toxicity NCI-CTCAE v5.0 Grade (unless otherwise specified)	Schedule Modification for Patritumab Deruxtecan
Mucositis oral	Grade 3	Delay patritumab deruxtecan until resolved to ≤Grade 1, and consider treatment per local practice/guidelines, then: 
 
• If resolved to ≤Grade 1 in ≤14 days, resume patritumab deruxtecan;
 
• If resolved to ≤Grade 1 in >14 days, then reduce patritumab deruxtecan by 1 dose level.
 

	Grade 4 (Life-threatening consequences; urgent intervention indicated)	Discontinue subject from patritumab deruxtecan.
Other Adverse Events (Non-laboratory or Laboratory)	Grade 3	Delay patritumab deruxtecan until resolved to ≤Grade 1, or baseline level, then: 
 
• If resolved in ≤7 days, resume patritumab deruxtecan;
 
• If resolved >7 days, then reduce patritumab deruxtecan by 1 dose level.
 

	Grade 4 (Life-threatening consequences; urgent intervention indicated)	Discontinue subject from patritumab deruxtecan.

ALT = alanine aminotransferase; ANC = absolute neutrophil count; AST = aspartate aminotransferase; CBC = complete blood count; CT = computed tomography; CTCAE = Common Terminology Criteria for Adverse Events; DNA = deoxyribonucleic acid; ECG = electrocardiogram; ECHO = echocardiogram; eCRF = electronic case report form; G-CSF = granulocyte colony stimulating factor; HBV = hepatitis B virus; HCV = hepatitis C virus; ILD = interstitial lung disease; INR = international normalized ratio; IV = intravenous; LVEF = left ventricular ejection fraction; MRI = magnetic resonance imaging; NCI = National Cancer Institute; NSAIDs = non-steroidal anti-inflammatory drugs; PK = pharmacokinetic; QTcF = corrected QT using Fridericia’s formula; RNA = ribonucleic acid; SpO2 = peripheral oxygen saturation; TBL = total bilirubin; ULN = upper limit of normal.

a There will be no dose interruptions for Grade 1 to Grade 3 lymphocyte count decreases. All dose interruptions must be based on the worst preceding toxicity.

During study treatment, subjects who develop systolic and/or diastolic hypertension that is deemed by the Investigator to be clinically significant should receive treatment with anti-hypertensive therapy according to the Investigator’s judgement and local institutional guidelines.

In addition, Investigators may consider dose reductions or discontinuations of the study drug according to the subject’s condition and after discussion with the study Medical Monitor or designee.

## 6.6. Prior and Concomitant Medications

Therapies used from the time the subject signs the main ICF for study participation to the 40-Day Follow-up Visit (+7 days) after the last administration of patritumab deruxtecan will be recorded in the eCRF. Prophylactic therapies (including any required premedication), prior therapies and all concomitant therapies will be recorded in the eCRF. Based on currently available clinical safety data for patritumab deruxtecan, it is recommended that subjects receive premedication with antiemetic agents. Refer to [Table 6.4](#).

All therapies received by the subjects within 35 days prior to enrollment will be recorded as prior therapies. Concomitant therapies include all prescription, over-the-counter, and herbal remedies.

### Therapies Requiring a Washout Period Before Enrollment

The following medications/therapies and products require a washout period before enrollment:

- Whole brain radiation therapy  $\geq 14$  days or stereotactic brain radiation therapy  $\geq 7$  days;
- Any cytotoxic chemotherapy, investigational agent or other anticancer drug(s) from a previous cancer treatment regimen or clinical study (other than EGFR TKI),  $\geq 14$  days or 5 half-lives, whichever is longer;
- Monoclonal antibodies, other than immune checkpoint inhibitors, such as bevacizumab (anti-VEGF) and cetuximab (anti-EGFR)  $\geq 28$  days;
- Immune checkpoint inhibitor therapy  $\geq 21$  days;
- Major surgery (excluding placement of vascular access)  $\geq 28$  days;
- Radiotherapy treatment to more than 30% of the bone marrow or with a wide field of radiation  $\geq 28$  days or palliative radiation therapy  $\geq 14$  days.
- Chloroquine or hydroxychloroquine  $> 14$  days.

### Prohibited Therapies/Products

The following medications/therapies and products will be prohibited during the Treatment Period through 40 days after the last dose of patritumab deruxtecan:

- Other anticancer therapy, including cytotoxic, immune checkpoint inhibitors, or targeted agents;
- Chloroquine and hydroxychloroquine;
- Live virus vaccination (beginning from 28 days prior to Cycle 1 Day 1);
- Other investigational therapeutic agents;
- Radiotherapy, except palliative radiation (as long as the radiation field does not include a measurable lesion or does not interrupt treatment for more than 28 days from the planned date of administration [ie, 49 days from the last infusion date]).
- Radiotherapy to the thorax is also prohibited. See “Permitted Therapies/Products” section below for exceptions on palliative radiation;
- Concomitant use of chronic systemic (IV or oral) corticosteroids (ie,  $> 10$  mg prednisone or equivalent anti-inflammatory) or other immunosuppressive medications except for managing AEs.

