ADA = anti-drug antibody; AE = adverse event; BICR = blinded independent central review; BM = biomarker; cfDNA = cell-free deoxyribonucleic acid; cfRNA = cell-free RNA; COVID-19 = coronavirus disease 2019; CQ = chloroquine; CR = complete response; CT = computed tomography; D = day; DNA = deoxyribonucleic acid; EC = Ethics Committee; ECD = extracellular domain; ECG = electrocardiogram; ECHO = echocardiogram; ECOG PS = Eastern Cooperative Oncology Group performance status; eCRF = electronic case report form; EGFR = epidermal growth factor receptor; EOT = end of treatment; ETDRS = Early Treatment Diabetic Retinopathy Study; FDG = fluorodeoxyglucose; HBsAg = hepatitis B surface antigen; HBV = hepatitis B virus; HCQ = hydroxychloroquine; HCV Ab = hepatitis C virus antibody; H&E = hematoxylin and eosin; HER3 = human epidermal growth factor receptor 3; HIV Ab = human immunodeficiency virus antibody; ICF = informed consent form; IHC = immunohistochemistry; IRB = Institutional Review Board; IV = intravenous; MRI = magnetic resonance imaging; MUGA = multigated acquisition; NGS = next generation sequencing; PET = positron emission tomography; PGx = pharmacogenetics; PK = pharmacokinetic(s); Post-I = Post-infusion; Pre-I = Pre-infusion; RECIST v1.1 = Response Evaluation Criteria in Solid Tumors version 1.1; RNA = ribonucleic acid; SAE = serious adverse event; SpO2 = peripheral oxygen saturation; TKI = tyrosine kinase inhibitor.

**Table 1.2: Schedule of Events for Cycle 4 and Subsequent Cycles of the Treatment Period, End of Treatment, and Follow-up Period**

		Cycle 4 and Subsequent Cycles Day 1		EOT a	40-Day Follow-up b	Long-Term Follow-up (Every 3 Months)	Comments
		Pre-I	Post-I				
Visit Window		±1D			+7D	±14 D	
End-of-Treatment Tumor Biopsy				X			An optional EOT tumor biopsy will also be performed at the time of progression or discontinuation from study treatment. Consent for this biopsy should be documented in the tissue consent portion of the appropriate ICF. Tumor biopsy should be obtained from primary tumor or metastatic site, preferably from a site of recent radiographic progression, within 40 days of the last dose of patritumab deruxtecan, and prior to starting any new anticancer treatment. See Section 8.7.2.

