MUGA = multigated acquisition; OS = overall survival; PET = positron emission tomography; PK = pharmacokinetic(s); Post-I = Post-infusion; Pre-I = Pre-infusion; RECIST v1.1 = Response Evaluation Criteria in Solid Tumors version 1.1; SAE = serious adverse event; SpO2 = peripheral oxygen saturation; TKI = tyrosine kinase inhibitor; TR= tumor requirement; Tx = treatment.

a This visit occurs within 7 days after the final dose of study treatment, or before starting new anticancer treatment, whichever comes first. If the decision to discontinue patritumab deruxtecan occurs >7 days after the final dose of patritumab deruxtecan, then this visit will occur within 7 days after the decision to discontinue patritumab deruxtecan or before the start of new anticancer treatment; whichever comes first. If the EOT Visit occurs  $\geq$ 40 days after the final dose of patritumab deruxtecan, the 40-Day F/U Visit does not need to be conducted.

b 40 days (+ 7 days) after the last study drug administration or before starting new anticancer treatment, whichever comes first.

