Subjects will continue to receive patritumab deruxtecan until documented disease progression per RECIST v1.1, clinical progression, unacceptable toxicity, withdrawal of consent by the subject, physician's decision, protocol deviation, pregnancy, lost to follow-up, study termination by the Sponsor, death, or other reasons. If progressive disease is suspected by Investigator tumor assessment, imaging must be submitted to BICR for expedited confirmation of disease progression. The decision to discontinue patritumab deruxtecan is according to Investigator judgement and should consider BICR assessment.

- The Follow-up Period will start upon permanent discontinuation of patritumab deruxtecan. After completion of the 40-day (+7 days) safety follow-up visit, subjects will be followed every 3 months for survival. Subjects who discontinue study treatment for any reason other than documented disease progression by BICR, death, lost to follow-up, or withdrawal of consent by the subject will continue to undergo tumor assessments at the same frequency of every 6 weeks ( $\pm 7$  days) from Cycle 1, Day 1 for the first 24 weeks then every 12 weeks ( $\pm 7$  days) during the Follow-up Period.

The primary analysis of ORR as assessed by BICR will be conducted after all enrolled subjects have either a minimum of 9 months of follow-up or have discontinued from the study earlier. The final analysis will occur after all subjects have discontinued from the study (see definition of overall End of Study [EOS] in Section 4.1.2).

The subject population is described in Section 5. A flow diagram of study activities is presented in Figure 1.1.

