## 7. STUDY DRUG DISCONTINUATION AND DISCONTINUATION FROM THE STUDY

### 7.1. Discontinuation of Study Drug

The primary reason for the permanent discontinuation of patritumab deruxtecan treatment administration must be recorded. Reasons for treatment discontinuation include:

- Death
- Adverse Event
- Progressive Disease per RECIST v1.1
- Clinical Progression: provide date (ie, definitive clinical signs of disease progression, but a recent radiographic assessment did not meet the criteria for PD according to RECIST v1.1)
- Withdrawal by the subject (**to discontinue study drug**) NOTE: In this section this is only withdrawal for treatment with study drug and is NOT the same thing as a complete withdrawal from the study. Discuss with the subject that they will remain in the study (ie, continue with study visits and assessments, including survival follow-up).
- Physician Decision
- Lost to Follow-up (see Section 7.3 for details on when a subject is considered Lost to Follow-up)
- Pregnancy
- Protocol Deviation
- Study Termination by Sponsor
- Other

After study drug is permanently discontinued for any reason other than death or lost to follow-up, the subject will be treated as clinically indicated by the Investigator or referring physician.

The Investigator must discuss with the subject that their decision to permanently discontinue the study drug means the subject still agrees to continue into the Follow-up Period for onsite or modified follow-up visits. Subjects will be followed for disease progression, if applicable, and survival at regularly scheduled intervals (see Table 1.2).

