### **Subsequent Anticancer Treatments**

Subsequent anticancer treatments taken since the EOT must be monitored and recorded in the eCRF until the end of the study.

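### Section 6.6 bars next-line anticancer and investigational treatment until 40 days after the last dose, with no exception for subjects who have permanently stopped study drug

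*Combined protocol and SAP*

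**What the plan says.** Section 6.6, under its heading on prohibited therapies, makes a list of items "prohibited during the Treatment Period through 40 days after the last dose of patritumab deruxtecan". The first item is other anticancer therapy, expressly including targeted agents. A separate item is "Other investigational therapeutic agents". The list does contain exceptions, for palliative radiation and for steroids or immunosuppressants used to manage adverse events. None concerns subjects who have stopped study drug for good.

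Section 4.1.1 ends the Treatment Period at permanent discontinuation: "The Follow-up Period will start upon permanent discontinuation of patritumab deruxtecan".

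Section 7.1 says that after permanent discontinuation, for any reason other than death or loss to follow-up, "the subject will be treated as clinically indicated by the Investigator or referring physician". It gives no timing and does not refer to Section 6.6.

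Table 1.2 footnote a says of the End of Treatment (EOT) visit: "This visit occurs within 7 days after the final dose of study treatment, or before starting new anticancer treatment, whichever comes first". It also waives the 40-Day Follow-up visit when the EOT visit falls 40 or more days after the final dose. Footnote b sets the 40-Day visit at 40 (+7) days "after the last study drug administration or before starting new anticancer treatment, whichever comes first".

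Section 10.1.9 allows deviations only where needed to remove an immediate hazard, and requires the sponsor to be told within 24 hours.

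**The concern.** A prohibition that outlasts the Treatment Period acts only on people no longer receiving study drug. In this trial most will have progressing metastatic or locally advanced NSCLC, and Section 2.3 puts median survival on standard therapy at about 10 months. For them the next step is other anticancer treatment or another trial, and Section 6.6 names both.

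A site that follows Section 6.6 to the letter delays that step. A site that follows Section 7.1 and starts sooner departs from the literal text of Section 6.6. No sentence says which section governs, so sites can handle identical subjects differently, and some starts may be logged as deviations while others are not.

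**Working it through.** **1. Which provisions need an early start?** Each is tested by asking whether it still has a function if every subject waits until day 41.

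| Provision | Function if next-line treatment waits until day 41 | Bearing |
|---|---|---|
| Section 7.1, treated as clinically indicated | Can be obeyed, but clinical judgement is then overridden by a rule it does not mention | Points to an earlier start |
| Footnote a, first part (EOT within 7 days, or before new treatment if sooner) | The second limb never applies, because it needs new treatment within 7 days of the final dose | Points to an earlier start |
| Footnote a, second part (decision to stop made more than 7 days after the final dose) | Works: a decision on day 38 and new treatment on day 41 fit | Neutral |
| Footnote b | Works: the visit window runs to day 47, so treatment on days 41 to 46 can bring the visit forward | Neutral |
| EOT biopsy, "within 40 days of the last dose of patritumab deruxtecan, and prior to starting any new anticancer treatment" | Both conditions can be met; the second is merely redundant | Neutral |
| Section 8.3, "Subsequent anticancer treatments taken since the EOT must be monitored and recorded in the eCRF until the end of the study" | Says when recording begins, not when treatment may begin | Neutral |

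Two provisions sit poorly with the literal rule. The rest fit either reading, and none expressly authorises an early start.

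**2. How long is the literal delay?** The plan gives no figure for this. Its related limits are consistent: 21 + 28 = 49 days from the last infusion for the maximum dose delay (Section 6.5), and 40 + 7 = 47 days for the on-treatment period (Section 9.5.2).

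Inputs: Cycle 1 Day 1 counted as day 0; doses due on days 0, 21 and 42; first scan at 6 weeks ±7 days, that is days 35 to 49; prohibition through day 40 after the last dose.

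Formula: days of prohibition remaining = 40 − s, with a floor of 0, where s is days since the last dose.

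- Dose given on day 42, progression found on days 43 to 49: s = 1 to 7, so 40 − 1 = 39 down to 40 − 7 = 33 days remain.
- Last dose on day 21, day-42 dose not given, scan on days 35 to 49: s = 35 − 21 = 14 to 49 − 21 = 28, so 40 − 14 = 26 down to 40 − 28 = 12 days remain.
- Study drug stopped after a dose delay, s = 40 to 49: 0 days remain.

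The overall range is 0 to about 39 days. Time spent on expedited central confirmation of progression (Section 4.1.1) counts towards s and shortens the remainder.

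**3. What would an earlier start do to the safety window?** Section 9.5.2 keeps the on-treatment period open to 47 days after the end of study treatment, taken here as the last dose, whatever new therapy is given. Days of next-line exposure inside it = 47 − start day.

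| Start of next-line treatment (days after last dose) | Days inside the 47-day window |
|---|---|
| 1 to 7 | 46 to 40 |
| 14 to 28 | 33 to 19 |
| 41 | 47 − 41 = 6 |

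**4. Primary endpoint.** Section 9.5.1.1 stops counting assessments for best overall response at progression or at the start of further anticancer treatment expected to affect response, whichever is earlier. An early start therefore does not contaminate ORR.

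**The case against.** The strongest reply is that the 40 days are a deliberate washout. Table 3.1 equates 40 days with five half-lives of the conjugate, and Section 6.6 itself asks for 14 days or five half-lives, whichever is longer, for earlier anticancer and investigational drugs at entry. The parallel is fair. But Table 3.1 attaches the figure to the time frame for collecting safety data, and no section offers it as a reason to withhold next-line care. If that was the intention, Section 7.1 should say so. What stands is that an earlier start can overlap residual study drug.

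A second reply is that the intention is plain: Section 7.1 deals specifically with subjects who have stopped, so care given under it follows the protocol. That is probably what was meant. It also means an early start is certainly a deviation only if Section 6.6 prevails, which the documents do not settle. That uncertainty is the reason to clarify.

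A reader might infer more: that the protocol contradicts itself, or that the biopsy rule and the recording rule in Section 8.3 also authorise early treatment. The documents do not support this. Waiting until day 41 satisfies every provision, and those two rules are compatible with waiting.

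**Conclusion.** The point holds as a minor one. Section 6.6, as written, keeps next-line and investigational treatment from subjects who have permanently stopped until day 41, while Section 7.1 and the first part of footnote a fit better with an earlier start.

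The literal delay is 0 to about 39 days, and 12 to 26 days in the case of first-scan progression with the day-42 dose not given. These figures assume on-schedule dosing in the first two cases and take no account of dosing-visit windows or central confirmation time. They are what the rule permits, not an observed delay. The documents give no rate of early next-line starts, so no number of affected subjects can be stated.

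A reader might also infer a threat to the primary result. There is none, because the rule for best overall response already handles new treatment. What is affected is patient care, consistency in recording deviations, and attribution of adverse events late in the 47-day window.

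**What to change.** In Section 6.6, after the list, add a sentence to this effect: *Once a subject has permanently discontinued patritumab deruxtecan, the bars on other anticancer therapy and on other investigational agents end at 40 days after the last dose or at the start of next-line treatment, whichever is earlier; the EOT visit and, unless waived under Table 1.2 footnote a, the 40-Day Follow-up assessments should be completed before next-line treatment starts.* The day-40 limit keeps a calendar end for subjects who decline site visits, and the reference to footnote a preserves its waiver. In Section 7.1, add a cross-reference to Section 6.6.

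In the adverse-event part of Section 9.5.2, keep the 47-day summary as planned and add a supplementary TEAE summary that excludes events starting on or after the first date of new anticancer treatment. Those treatments are already recorded under Section 8.3.

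The cost is two short text changes and one extra table, in a protocol amendment. The downside is that more next-line exposure may fall inside the 47-day window and overlap residual study drug. This matters because Table 3.1 labels safety a primary outcome measure. The supplementary summary makes the mixing visible but does not remove it from the main tables. The other prohibitions, including radiotherapy, stay as they are.
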